In terms of toxicity, 9 patients discontinued treatment between weeks 25 and 49—4 due to AEs including 2 deaths, 1 protocol violation, 2 to progressive disease, and 2 withdrawn. Overall there were 7 SAE's but none drug related, and 3 deaths, none drug related. There were no seizures reported. The most frequent treatment-emergent AEs were gynecomastia (47.8%), fatigue (38.8%), nipple pain (19.4%), and hot flash (17.9%)—grade 1 or 2 severity. Others included diarrhea (11.9%), hypertension (11.9%), nausea (10.4%, and pain in extremity (10.4%). The overall rate of treatment associated AE's was 95.5%. Global health status by EORTC QLQ-C39 was unchanged from baseline to week 49, however fatigue was increased from 11.3 (SD-17.2) to 14.0 (SD-14.3) with a moderate deterioration of sexual activity functional scale of -9.8 (SD-18.0) from 28.6 (SD-24.6) baseline.

The overall conclusions were that: 1) large reductions in PSA were maintained beyond 25 weeks, 2) PSA control maintained in patients continuing to 49 weeks, 3) bone mineral density and other metabolic variables (fat body mass, lipid, glycemic profile) were not impacted, and 4) hormone level changes and common drug related AE's were consistent with potent AR inhibition. In this setting, of course, the risks and benefits would be compared to standard LHRH agonist therapy which carries risks of hot flashes and loss of libido in nearly all patients, and other side effects such as depression, fatigue, decreased bone mineral density, increased fracture risk, obesity, risk of diabetes, and risk of cardiovascular disease.

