4. INVESTIGATIONAL PLAN

This is a single center, phase II, open label, pre-operative study of apalutamide in patients with intermediate risk prostate cancer. The study period will consist of screening, treatment, and follow-up visits to 12 months post-operative. Additional follow-up onsite or via remote contact will determine disease-free and treatment-free status at yearly intervals 2-5. Surgery will occur within 2 weeks of completing 24 weeks of apalutamide. At the mid-way evaluations (weeks 9 or 12), patients who fail to reach a ≥50% decrease in PSA, or demonstrate suspicious changes in DRE will be considered non-responders and recommended for early surgery. For responders, the plan calls for 5 pre-operative PSA measurements that will be analyzed for rate of decline and nadir. In the post-treatment evaluation, patients will be off formal protocol at 12 months, however the investigating team will track PSA measurements for biochemical failure rates at 2, 3, 4 and 5 years (outside or inside measurements) using >0.2 ng/mL as the failure definition.

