6.1. Endpoints of Study

6.1.1. **Primary Endpoint**

The primary endpoint, aggregate pathologic risk features, is defined as any of the 3 pathologic staging features on a radical prostatectomy specimen that indicate elevated future risk of a patient needing pelvic radiation therapy. It can be any single or combination of the three. The three drivers per AUA/ASTRO guidelines are positive surgical margins, extraprostatic extension, and/or seminal vesicle invasion. These will be determined by a single expert genitourinary pathologist. The primary objective is to show a 20% decrease in these aggregate pathologic features.

6.1.2. **Secondary Endpoints**

- To determine safety and tolerability of 6 months neoadjuvant apalutamide followed by radical prostatectomy for intermediate risk prostate cancer
- To estimate the frequency of clinical complete responses (pT0) and "near" complete responses (<6mm total tumor volume)
- To characterize molecular features of treated prostate cancer and link them to morphologic characterization
- To measure 3-5 year biochemical recurrence rate and quality of life of treated patients as a baseline to inform a larger phase III trial.

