6.2 Analysis Plan

All patients who receive at least 9 weeks of neoadjuvant therapy of apalutamide and undergo radical prostatectomy will be evaluable for the primary endpoint of APRF. The proportion of patients with APRF will be estimated by the number of patients with APRF divided by the total number of evaluable patients. As a primary analysis, we will estimate this proportion along with the exact 95% confidence interval. All patients who receive any dose of apalutamide will be evaluable for safety. Toxicity data will be summarized by category, grade and attribution. Frequency distributions, graphical techniques and other descriptive measures will form the basis of the analysis of safety data.

The proportion of patients having clinical complete responses and "near" complete responses will be estimated, along with the exact 95% confidence interval. The molecular features of the treated patients will be characterized using descriptive statistics and their association with the primary endpoint, APRR, or

clinical response will be assessed through logistic regression analyses. The Kaplan-Meier method will be used to assess time to biochemical recurrence and to estimate the rate of biochemical recurrence at various time points. The EPIC quality of life data will be summarized by domains and will be compared pre- and post-treatment using paired t-test or Wilcoxon signed rank test as appropriate.

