- Concomitant Medications Review
- Adverse Events

Note: At the mid-way evaluation (week 9), patients who fail to reach a 50% decrease in PSA, or demonstrate suspicious changes in DRE will be considered non-responders and recommended for early surgery.

4) Week 12 Procedures (± 3 days):

Optional: Repeat prostate biopsy per urologist's discretion. Acceptable to perform at the week 9 or week 17 visit if requested for patient travel needs.

5) Week 17 Procedures (± 3 days):

- Medication dispensing (neoadjuvant apalutamide)
- Dosing compliance
- Physical exam with DRE if indicated by treating physician
- Vital signs
- ECOG Performance Status
- Laboratories (Serum chemistry and hematology)
- Thyroid Stimulating Hormone (TSH) (T3 and T4 only to be done if TSH is abnormal)
- Prostate-Specific Antigen (PSA) Test and Testosterone
- Concomitant Medications Review
- Adverse Events
- EPIC Quality of Life (QOL) Questionnaire
- Blood collection for Correlative Studies

6) Week 24/ Pre-op/ End of Treatment Visit Procedures (± 3 days):

- Dosing compliance
- Physical exam with DRE
- Vital signs
- ECOG Performance Status
- Laboratories (Serum chemistry and hematology)
- Thyroid Stimulating Hormone (TSH) (T3 and T4 only to be done if TSH is abnormal)
- Prostate-Specific Antigen (PSA) Test and Testosterone
- Concomitant Medications Review
- Adverse Events
- EPIC Quality of Life (QOL) Questionnaire

- Blood collection for Correlative Studies
- 7) Radical Prostatectomy (2 weeks (+/-7 days) after last dose of study drug):
 - Perioperative data collection
 - Pathology Tissue Collection

C. Follow-up Phase:

- 1) Post Radical Prostatectomy: (within 30 days post-op +/- 3 days)
 - Physical exam and DRE if indicated by treating physician
 - Assess complications from surgery at 30 days using Clavien methodology (Table 5).
 - Adverse Events
 - Epic Quality of Life (QOL) Questionnaire
 - PSA, testosterone
- 2) Six Months Post-Radical Prostatectomy: (+/- 4 weeks)
 - a. Update complications to 90 day window
 - b. Use of adjuvant/salvage therapies
 - c. EPIC Quality Of Life (QOL) Questionnaire
 - d. PSA, testosterone
- 3) Twelve Months Post Radical Prostatectomy—Last on-site Study Visit: (+/- 4 weeks)
 - a. EPIC Quality Of Life Questionnaire
 - **b.** PSA, testosterone
 - c. Use of adjuvant/salvage therapies
 - d. Update complications
- 4) Post Study Follow-up Data Collection (on-site or remote): (+/- 4 weeks)
 - **a.** Intervals 24, 36, 48, 60 months

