 - **b.** PSA/biochemical relapse-free status
 - **c.** Use of adjuvant/salvage therapies
 - d. Update complications
 - e. Epic Quality of Life (QOL) Questionnaire

7.2 Details of Assessment Methods:

7.2.1 QOL assessments per above: may be written or via tablet. Surveys will consist of the Expanded Prostate Cancer Index (EPIC), including the SF-12. As an alternative, the data may be collected using an electronic tablet method. Any post-operative surveys occurring after the incidence of additional post radical prostatectomy radiation or hormonal therapy will continue but be so designated for analysis.

2015-0693 June 10, 2022 Page 21

7.2.2 Complications: use Clavien reporting system shown in Table 5.

Table 5: Classification of Surgical Complications [34]

Grades	Definition
Grade I	Any deviation from the normal postoperative course without the need for pharmacological treatment or surgical, endoscopic and radiological interventions. Allowed therapeutic regimens are: drugs such as antiemetics, antipyretics, analgesics, diuretics and electrolytes, and physiotherapy. This grade also includes would infections opened at the bedside.
Grade II	Requiring pharmacological treatment with drugs other than such allowed for grade I complications. Blood transfusions and total parenteral nutrition are also included.
Grade III	Requiring surgical, endoscopic or radiological intervention
Grade IIIa Grade IIIb	Intervention not under general anesthesia. Intervention under general anesthesia.
Grade IV	Life-threatening complication (including CNS complications)* requiring IC/ ICU management.
Grade IVa Grade IVb	Single organ dysfunction (including dialysis) Multiorgan dysfunction
Grade V	Death of a patient
Suffix "d"	If the patient suffers from a complication at the time of discharge, the suffix "d" (for "disability") is added to the respective grade of complication. This label indicates the need for a follow-up to fully evaluate the complication.
excluding trans	nage, ischemic stroke, subarachnoid bleeding, but sient ischemic attacks, CNS, central nervous system; IC, are; ICU, intensive care unit.

2015-0693 June 10, 2022 Page 22

Table 6: Study Calendar

Evaluation	Screeninga	Wk 1	Wk 5	Wk 9	Wk 12	Wk 17	Wk 24/ Preop ^h	Surgery	30 d post op	6 mo	12 mo	2 yr	3 yr	4 yr	5 yr
			+/- 3 days		+/- 3 days	+/- 4 wks	+/-4 wks	+/-4 wks	+/-4 wks	+/- 4 wks	+/-4 wks				
Medical History	Х														
Physical Exam w/DRE	Х	Хр	Χp	Х		Хр	Х		Χþ						
Vital Signs	Х	Х	Χ	Χ		Х	Х								

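### EPIC is tested only by a paired pre/post comparison with no named visits: name the contrasts and use a repeated-measures model

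*Combined protocol and SAP*

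**What the plan says.** Section 6.2 makes two statements about EPIC. One is descriptive: "The EPIC quality of life data will be summarized by domains". The other is the only planned test: the scores "will be compared pre- and post-treatment using paired t-test or Wilcoxon signed rank test as appropriate". It names no visits and gives no rule for missing surveys.

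Section 7.1 and Table 6 schedule EPIC ten times: at screening, week 17 and week 24 before surgery, then at 30 days, 6 months and 12 months after it, and in long-term follow-up at "Intervals 24, 36, 48, 60 months".

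The wording points two ways. Section 7.1 heads the last pre-surgery visit "Week 24/ Pre-op/ End of Treatment Visit Procedures (± 3 days", which ties the end of treatment to the end of apalutamide. Section 4 applies the same language to follow-up after surgery: "In the post-treatment evaluation, patients will be off formal protocol at 12 months".

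Section 7.2.1 says surveys completed after post-operative radiation or hormonal therapy "will continue but be so designated for analysis", but section 6.2 makes no use of that designation. Note h to Table 6 has early discontinuers complete the pre-operative assessments, EPIC among them, within 30 days of stopping, as their last study visit. Section 6.1.2 gives the aim as measuring "quality of life of treated patients as a baseline to inform a larger phase III trial".

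**The concern.** Two separate weaknesses sit in one sentence.

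The first is the contrast. If the later survey is week 24, the change covers the drug period only. If it is a post-operative survey, the change combines apalutamide with prostatectomy. The plan leaves the choice open until the data are in hand.

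The second is the method. A paired test uses only men who completed both surveys. A man with screening and week 17 scores but no week 24 score contributes nothing, although his week 17 score is informative about the missing one. If men who are faring worse return fewer surveys, the completers look better than the whole group.

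This matters because section 1.1 favours apalutamide monotherapy over LHRH-agonist or abiraterone treatment on grounds of sexual function, and the EPIC results are meant to inform a phase III trial. Without a control arm, a contrast that stays before surgery is the cleanest evidence on tolerability that this trial can give, and the plan does not commit to it.

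**Working it through.** **1. Figures in the plan.** There is no sample size, power or missing-data figure for EPIC. The only power statement is for the primary endpoint (41 patients, 35% against 15%, 84%). It reproduces: rejecting at 8 or fewer of 41 gives a lower-tail error of 0.0240 and power of 84.8%. Nothing below affects it.

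**2. What the wording allows.** EPIC surveys: 3 before surgery + 7 after = 10. Screening to week 24 fits the sentence in 6.2 under the visit heading in 7.1. Screening to any of the seven later surveys fits it under the usage in section 4. The contrast is therefore undefined.

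**3. Inputs for an illustration.** The only quality-of-life change with an SD in the documents is in section 2.5, for enzalutamide monotherapy: a "moderate deterioration of sexual activity functional scale of -9.8 (SD-18.0) from 28.6 (SD-24.6) baseline". That is an EORTC scale at week 49 on another drug, so it sets a scale and nothing more. With equal variances at both visits, the implied correlation is

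rho = 1 - 18.0²/(2 × 24.6²) = 1 - 324/1210.32 = 0.732.

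For reference, with all 45 pairs the 95% confidence half-width is t × 18/√45 = 2.015 × 18/6.708 = 5.4 points.

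**4. Simulation.** 45 men; screening, week 17 and week 24; SD 24.6, correlation 0.73 and a true change of -9.8 at both later visits. The missing rate and mechanism are assumptions, because the documents give neither. The complete-pairs mean is compared with the likelihood estimate that a three-visit repeated-measures model gives. Bias in points (positive means the fall is understated), 8,000 runs per cell, with the log-odds of missing week 24 rising by 1 for each 18-point larger fall:

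| Missingness depends on | Week 24 missing | Complete pairs | Model |
|---|---|---|---|
| nothing (completely random) | 10 / 20 / 30% | about 0 | about 0 |
| observed week 17 change | 10 / 20 / 30% | +0.8 / +1.6 / +2.3 | at most 0.1 |
| unseen week 24 change | 10 / 20 / 30% | +1.7 / +3.1 / +4.5 | +1.3 / +2.3 / +3.4 |

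With a slightly weaker dependence on the week 17 change (log-odds 0.05 per point) and lower rates, the complete-pairs estimates are:

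- 6% missing: -9.4, a bias of 9.8 - 9.4 = 0.4 (0.4 to 0.5 across runs)
- 14% missing: -8.8, a bias of 1.0
- 23% missing: -8.1, a bias of 1.7

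The model gives -9.7 to -9.9 throughout. The standard error is 2.8 to 3.0.

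**5. Precision.** Under completely random loss of 30%, the standard error is 3.21 for pairs and 3.07 for the model. When missingness depends on week 17, the two are practically equal (2.94 and 2.97 at 20%). The gain is in bias rather than precision.

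**6. Size of the model.** An unstructured covariance has 3 × 4/2 = 6 parameters for the three pre-surgery visits, but 10 × 11/2 = 55 for all ten, per domain, from at most 45 men.

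**The case against.** The strongest reply is that this needs only a line of clarification. The week 24 visit carries the end-of-treatment label, and the discontinuation criteria in section 8.2.4 use study treatment to mean apalutamide. Screening to week 24 is then a natural reading and contains no surgery. A reader might infer that the planned test certainly mixes drug and prostatectomy; the documents do not support that. Nor can such mixing be sized, since they give no EPIC change for surgery alone. A combined change may even be intended, because the objective concerns treated patients.

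A reader might also infer that a repeated-measures model cures both weaknesses. It does not. Naming the visits settles the contrast, and a paired test of screening against week 24 would isolate the pre-surgery period equally well. The model addresses only missing surveys, and fully only if missingness depends on observed scores. A man with a screening survey alone, such as a week 9 non-responder who goes to early surgery and returns no pre-operative survey, adds almost nothing.

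Losses may also be small. In the enzalutamide study of section 2.5, 94% completed 25 weeks, and note h to Table 6 schedules a pre-operative survey for early discontinuers. At 6% missing the bias is about half a point.

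These replies limit the size of the problem. They do not supply a defined contrast, a rule for missing surveys, or a use for the section 7.2.1 flag. The data for a better analysis are already being collected.

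**Conclusion.** The concern holds in a limited form. The sole EPIC test leaves its contrast undefined, so it may combine drug and surgery. It also discards men with one survey missing and the week 17 information. Under the assumed mechanism the fall is understated by 0.4/9.8 = 4% at 6% missing and 1.7/9.8 = 17% at 23%. That is real but modest beside a standard error of about 3 points. It rests on an assumed missing rate and mechanism, and on SDs from another scale, drug and time point.

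Three stronger conclusions should not be drawn:

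- Week 24 minus screening is not a pure drug effect. In a single-arm trial it is drug plus time.
- The model does not guarantee an unbiased answer: at 20% missing by the unseen score, the bias falls only from +3.1 to +2.3.
- Nothing in the documents settles that surveys after radiation or hormones should be left out of the main post-operative result. That is a choice between two questions, and both answers can be reported.

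Quality of life is a secondary objective, and the primary analysis is untouched.

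**What to change.** Replace the test sentence in section 6.2 with a plan along these lines:

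- **Pre-surgery contrast.** For each EPIC domain, fit a likelihood-based repeated-measures model to screening, week 17 and week 24/pre-operative scores, with visit as a factor and unstructured covariance, in all treated men with a screening survey. Report week 24/pre-operative minus screening as the change during drug treatment, noting that it is drug plus time.
- **Post-operative contrasts.** Report screening to each named post-operative visit separately, as the change under the whole strategy. Use a simpler covariance or visit-by-visit models, not an unstructured ten-visit matrix.
- **Flagged surveys.** Give post-operative results with and without surveys completed after radiation or hormonal therapy.
- **Early discontinuers.** State whether their pre-operative survey counts as the week 24/pre-operative score. The 30-day window in note h is longer than the planned interval from last dose to surgery, so also say how a survey dated after the operation is classed.
- **Checks.** Keep the paired t or Wilcoxon test as a check, and add a sensitivity analysis in which missing scores are assumed worse than the model predicts.

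The cost is SAP wording, slightly more modelling and an explicit missing-at-random assumption for the main result. No new data are needed, and the 41 evaluable and 45 enrolled patients stand.

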6.3 Interim Analysis

The standard therapy for intermediate risk prostate cancer patients is radical prostatectomy. In the current trial, we are treating patients with apalutamide for 6 months in the neoadjuvant setting followed by the standard radical prostatectomy, thus we do not anticipate the rate of APRF(aggregate pathologic risk features) to be higher than the 35% rate with radical prostatectomy alone. Therefore, no interim analysis for futility is planned.

Monitoring for safety will be implemented in this single arm trial with the benchmark of avoiding extreme toxicities (TOX), defined as any adverse event preventing surgery or treatment-related death before surgery. Patients who voluntarily leave the trial for any reasons, or are successfully treated with dose reductions and proceed with surgery will not be counted as having a TOX. Denote the probability of TOX by θ_T and a beta(0.6, 1.4) distribution was assumed for the prior. Our stopping rule is given by the following probability statement: Pr ($\theta_T > 0.30$ | data) >0.90. That is, we will stop the trial if, at any time during the study, we determine that there is more than a 90% chance that the TOX rate is more than 30%. The corresponding stopping boundaries are shown in Table 1 below and the operating characteristics of the toxicity monitoring are illustrated in Table 2. Multc Lean Desktop (v2.1.0) was used for generating the stopping boundaries and the OC table.

Table 1. Interim toxicity stopping boundaries in cohort size of 5.

Among These Number of	Stop the trial if these many
Patients	patients with toxicities
5	4-5
10	6-10
15	8-15
20	9-20
25	11-25
30	13-30
35	15-35
40	16-40
45	18-45

Table 2. The operating characteristics of toxicity monitoring.

True Toxicity Rate	Prob (stop early)	Average number of patients
0.1	0.0006	44.98
0.2	0.02	44.32
0.3	0.21	39.70
0.4	0.66	28.55
0.5	0.95	17.57

An Efficacy/Toxicity Summary will be submitted after the first five evaluable patients complete 24 weeks of study treatment, and every five patients thereafter. The Investigator is responsible for completing the summary report and submitting it to the IND Office Medical Monitor for review.

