- Important medical events that may not result in death, be life-threatening, or require hospitalization may be considered a serious adverse drug experience when, based upon appropriate medical judgment, they may jeopardize the patient or subject and may require medical or surgical intervention to prevent one of the outcomes listed in this definition. Examples of such medical events include allergic bronchospasm requiring intensive treatment in an emergency room or at home, blood dyscrasias or convulsions that do not result in inpatient hospitalization, or the development of drug dependency or drug abuse (21 CFR 312.32).
- Important medical events as defined above may also be considered serious adverse events. Any important medical event can and should be reported as an SAE if deemed appropriate by the Principal Investigator or the IND Sponsor, the IND Office.

NOTE: DEATH FOR ANY REASON SHOULD BE REPORTED AS A SERIOUS ADVERSE EVENT.

Hospitalization

For reports of hospitalization, it is the sign, symptom or diagnosis which led to the hospitalization that is the serious event for which details must be provided.

Any event requiring hospitalization or prolongation of hospitalization that occurs during the study must be reported as a serious adverse event, except hospitalizations for the following:

- Hospitalizations not intended to treat an acute illness or adverse event (e.g., social reasons such as pending placement in long-term care facility)
- Surgery or procedure planned before entry into the study. [Note:
 Hospitalizations that were planned before the start of data collection and
 where the underlying condition for which the hospitalization was planned has
 not worsened will not be considered serious adverse events. Any adverse
 event that results in a prolongation of the originally planned hospitalization is
 to be reported as a new serious adverse event.]

Life-Threatening Conditions

Disease progression should not be recorded as an adverse event or serious adverse event term; instead, signs and symptoms of clinical sequelae resulting from disease progression/lack of efficacy will be reported if they fulfill the serious adverse event definition.

Unexpected (Unanticipated) AE - Any AE, with specificity or severity that is not consistent with the current IB, or the applicable product reference safety information, or not consistent with the risk information described in the informed consent document or general investigational plan.

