8.2.2. Attribution Definitions

The following classification will be used to determine whether an AE is related to the study drug, CT-011:

- Definite It is clearly related
- Probable It is likely related
- Possible It may be related
- · Unlikely It is doubtfully related
- Unrelated It is clearly NOT related

Definitely related – Events directly or indirectly attributed to study drug, and/or study participation. Events occurring with sufficient frequency to suggest that they are not random. The event follows a temporal sequence from the time of drug administration and follows a known response pattern to the study drug. It occurs immediately following the study drug administration, improves on stopping the drug, or reappears on repeat exposure.

Probably related – The event follows a reasonable temporal sequence from the time of drug administration, and follows a known response pattern to the study drug and cannot be reasonably explained by other factors. There is a reasonable response to withdrawal of the drug. Rechallenge information is not available or advisable.

Possibly related – The event has a reasonable temporal relationship to the study drug administration and follows a known response pattern to the study drug. However, a potential alternate etiology may be responsible for the event. The effect of drug withdrawal is unclear. Rechallenge information is unclear or lacking.

Unlikely – The adverse event is doubtfully related to the investigational agent.

Unrelated – Events that would occur regardless of study participation, including events that are clearly random occurrences. If the frequency of the event suggests a possible connection to the study intervention, then it should be considered related. If the event is clearly related to other factors, such as a patient's clinical

state, therapeutic interventions, or concomitant medications, the event would be considered unrelated to therapy.

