8.2.4. Adverse Events Reporting

All Adverse Events

General guidelines – Toxicity will be scored using CTC AE Version 4.0 for toxicity and adverse event reporting. A copy of the CTCAE Version 4.0 can be downloaded from the CTEP homepage (http://ctep.info.nih.gov). All appropriate treatment areas should have access to a copy of the CTC AE Version 4.0. All adverse clinical experiences must be recorded according to the table "Recommended Adverse Events Recording Guidelines", after they were documented in the treating

2015-0693 June 10, 2022 Page 31

physician's clinic note, utilizing the NCI CTC v 4.0 to determine terminology and grade. Adverse events will be recorded following the first exposure to study drug until 30 days following the last administration of study treatment or study discontinuation/termination, whichever is earlier. For discontinued patients, follow up on serious adverse events will be conducted up to 30 days from last treatment of study drug.

When an adverse event occurs, the following information and assessments should be recorded:

- i) The signs, symptoms, or diagnosis of the event.
- ii) The date of the event.
- iii) The adverse event severity, using the criteria outlined above.
- iv) The relationship of the event to the study drug as outlined above.
- v) The description of any action taken regarding study drug disposition.
- vi) Any required therapy, medication, treatment, or diagnostic procedure.

The Principal Investigator (PI) or physician designee is responsible for the appropriate medical management of all adverse events. The PI or physician designee must evaluate each adverse experience for its seriousness and determine attribution to study drug.

The investigator must appraise all abnormal laboratory results for their clinical significance. If any abnormal laboratory result is considered clinically significant, the investigator must provide details about the action taken with respect to the test drug and about the patient's outcome.

The investigator must appraise all evaluation test results for their clinical significance. If any abnormal evaluation test result is considered clinically significant, the investigator must provide details about the action taken with respect to the test drug and about the patient's outcome. Any evaluation test that is not considered clinically significant will not be captured as an adverse event (AE).

Serious Adverse Events

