All events occurring during the conduct of a protocol and meeting the definition of a SAE must be reported to the IRB in accordance with the timeframes and procedures outlined in "The University of Texas M. D. Anderson Cancer Center Institutional Review Board Policy for Investigators on Reporting Unanticipated Adverse Events for Drugs and Devices". Unless stated otherwise in the protocol, all SAEs, expected or unexpected, must be reported to the IND Office, regardless of attribution (within 5 working days of knowledge of the event).

All life-threatening or fatal events, that are unexpected, and related to the study drug, must have a written report submitted within **24 hours** (next working day) of knowledge of the event to the Safety Project Manager in the IND Office.

Unless otherwise noted, the electronic SAE application (eSAE) will be utilized for safety reporting to the IND Office and MDACC IRB.

Serious adverse events will be captured from the time of the first protocol-specific intervention, until 30 days after the last dose of drug, unless the participant withdraws consent. Serious adverse events must be followed until clinical recovery is complete and laboratory tests have returned to baseline, progression of the event has stabilized, or there has been acceptable resolution of the event. Additionally, any serious adverse events that occur after the 30 day time period that are related to the study treatment must be reported to the IND Office. This may include the development of a secondary malignancy.

Reporting to FDA:

Serious adverse events will be forwarded to FDA by the IND Sponsor (Safety Project Manager IND Office) according to 21 CFR 312.32.

It is the responsibility of the PI and the research team to ensure serious adverse events are reported according to the Code of Federal Regulations, Good Clinical Practices, the protocol guidelines, the sponsor's guidelines, and Institutional Review Board policy.

Maintenance of Safety Information:

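### With no other counted toxicity, the section 6.3 stopping rule never requires a stop for one treatment-related death, and no other protocol text requires a pause in enrolment after one

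*Combined protocol and SAP*

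**What the plan says.** Section 6.3 contains the only trial-level toxicity stopping rule. A TOX is "defined as any adverse event preventing surgery or treatment-related death before surgery". The TOX rate has a beta(0.6, 1.4) prior, and the trial stops if the posterior probability of a rate above 0.30 exceeds 0.90. The text says "we will stop the trial if, at any time during the study" this is met. Table 1 of that section lists boundaries only at every fifth patient, starting at 4 of 5. A periodic efficacy and toxicity summary is first due once five evaluable patients have completed 24 weeks, and the investigator is responsible for "submitting it to the IND Office Medical Monitor for review".

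Section 8.2 handles individual deaths:

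- Section 8.2.1: "DEATH FOR ANY REASON SHOULD BE REPORTED AS A SERIOUS ADVERSE EVENT".
- Section 8.2.2 grades attribution from definite to unrelated. The lowest grade above unlikely is "Possible It may be related".
- Section 8.2.4: the investigator or a physician designee "must evaluate each adverse experience for its seriousness and determine attribution to study drug".
- Section 8.2.4: a written report within 24 hours (next working day) covers "All life-threatening or fatal events, that are unexpected, and related to the study drug". The clock runs from the time "of knowledge of the event to the Safety Project Manager in the IND Office", who receives it. Other serious events go to the IND Office within 5 working days. Serious events also go to the IRB, to FDA, and to the drug supplier within 24 hours.

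**The concern.** A 30% tolerance can be reasonable for adverse events that keep a man from surgery. It is far too loose to respond to drug-related death, yet the definition pools the two with equal weight. Section 6.3 itself notes that standard therapy for these men is radical prostatectomy, which does not need the study drug. If a death is judged related to apalutamide and 6.3 is followed as written, the next man may start the drug and men already taking it may continue. The only step the protocol requires first is the investigator's own evaluation and reporting. What is at stake is exposure of further men between a drug-related death and a considered decision to go on.

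**Working it through.** **Inputs.** Prior beta(0.6, 1.4), rate threshold 0.30, probability cut-off 0.90, and Tables 1 and 2: section 6.3. Maximum of 45 men: section 6. Treatment-related death rate: not given, so 0.5%, 1% and 2% are assumed.

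**Step 1: reproduce the plan's figures.** After x TOX in n patients the posterior is beta(0.6 + x, 1.4 + n − x). The boundary at n is the smallest x with Pr(rate > 0.30) > 0.90.

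- At n = 5, 10, 15, …, 45 this gives 4, 6, 8, 9, 11, 13, 15, 16, 18: all nine Table 1 boundaries.
- Exact binomial recursion with looks every five patients, not counting a stop at 45 as early, gives stopping probabilities of 0.0006, 0.0223, 0.2116, 0.6566 and 0.9458 at true rates 0.1 to 0.5. Mean sample sizes are 44.98, 44.32, 39.70, 28.55 and 17.57. Both rows match Table 2.

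**Step 2: deaths only, no other TOX.**

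| Deaths / patients counted | Posterior Pr(rate > 0.30) | Stop required? |
|---|---|---|
| 1/1 | 0.789 | no |
| 1/2 | 0.629 | no |
| 2/2 | 0.928 | yes, if checked here |
| 2/3 | 0.838 | no |
| 2/4 | 0.734 | no |
| 2/5 | 0.626 | no |
| 3/5 | 0.875 | no |
| 4/5 | 0.975 | yes |

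For a fixed number of deaths the posterior falls as n grows, so 0.789 is the most that one death can produce. Checked after every patient, the boundary is 2 at n = 2, 3 at n = 3 and 4, and 4 at n = 5 to 7. Two deaths alone therefore cross only at n = 2. At the five-patient looks the boundary is never below 4, so three deaths alone never cross.

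**Step 3: size under assumed death rates p, 45 men.** P(at least one) = 1 − (1 − p)^45. P(at least two) also subtracts 45p(1 − p)^44. The last two columns use the Step 1 recursion with deaths as the only TOX.

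| p | At least one death | At least two | Rule triggered, every-patient checks | Rule triggered, five-patient looks |
|---|---|---|---|---|
| 0.5% | 20% | 2.1% | 0.000025 | 3.1 × 10⁻⁹ |
| 1% | 36% | 7.5% | 0.00010 | 5.0 × 10⁻⁸ |
| 2% | 60% | 23% | 0.00042 | 8.0 × 10⁻⁷ |

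The last two columns assume patients are counted in enrolment order. The enzalutamide monotherapy study in section 2.5 enrolled 63 patients and had three deaths, none drug related. Zero in 63 leaves a one-sided 95% upper limit of 1 − 0.05^(1/63) = 4.6%, so it does not exclude the assumed range.

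**Step 4: look for a pause elsewhere.** The 8.2.1 to 8.2.4 provisions are duties to classify, attribute and report. The dose-modification, discontinuation and withdrawal rules in 8.2.4 act on individual patients. The only item that the protocol sends to the Medical Monitor by name is the periodic summary, whose timing follows completed patients and not a death. No text makes enrolment wait.

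**The case against.** The strongest reply is that nothing in the plan is broken. Section 6.3 is a rate monitor with stated operating characteristics that reproduce. A rule tuned to 30% is not meant to react to one event, and no text promises that it will. Single deaths are left to case-level safety reporting, which is extensive. This stands as far as it goes: there is no calculation error, and the point concerns a design choice.

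A reader might infer that a drug-related death would pass without review. The documents do not support that. The investigator or designee must evaluate and attribute it, and it reaches the IRB, IND Office, FDA and supplier, any of which may act. The IRB policy and 21 CFR 312.32, which 8.2.4 refers to, are not reproduced, so whether they would lead to a pause in practice cannot be judged here. What remains is that the protocol itself requires neither a pause nor an independent review before the next man starts.

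A reader might also infer that two deaths require a stop only if they are the first two men enrolled. That goes too far. Section 6.3 does not say whether men still on treatment are counted. If only known outcomes count, early deaths enter the denominator ahead of men still in their 24 weeks, and 2 of 2 could arise later in enrolment. The small trigger probabilities would then change. The one-death result would not, because 1 of 1 is already the most extreme case.

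Two further limits are fair. Deaths add to other TOX: two deaths plus two surgery-preventing events among the first five men meet the 4 of 5 boundary. And the 24-hour IND Office report misses a related death only if it counts as expected, which depends on reference safety information not included here.

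**Conclusion.** The point holds in a limited form. The written stopping rule gives no protection specific to drug-related death. With no other TOX, one death never requires a stop under any denominator. Two require one only as the first two patients counted with every-patient checking, and three do not at the Table 1 looks. The discretion of outside bodies is the only remaining trial-level safeguard, and the protocol does not make it a condition of further enrolment.

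The posteriors follow exactly from the stated prior and threshold. The 20% to 60% range rests entirely on assumed death rates, and the one monotherapy precedent, with a different drug, gives reason to expect a low risk. This is a low-probability gap to consider closing. It is no reason to change the design or recalculate the tables.

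**What to change.** Keep the TOX rule and Tables 1 and 2. Add to section 6.3:

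> Any death before surgery judged possibly, probably or definitely related to apalutamide, whether expected or not, is reported to the IND Office Medical Monitor within 24 hours. New enrolment pauses until the Medical Monitor has reviewed the death and decided whether enrolment may resume. Within [number] days the Medical Monitor also decides whether men already on treatment continue dosing.

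The sponsor should fill in the number of days. Dosing is not halted automatically, so the deadline is what protects men already on the drug.

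The cost is this clause and one additional 24-hour notice. It uses the existing Medical Monitor role and the 8.2.2 attribution grades, and needs no new committee, boundaries or patients. The downside is a possible accrual pause, including for a death graded possible and later judged unrelated. Because that trigger is broader than treatment-related death, its rate may be higher. If the rate of deaths judged at least possibly related were 0.5%, 1% or 2%, the clause would be used at least once in 45 men with probability 20%, 36% or 60%. If no such death occurs it is never used.
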